4.2 Exclusion criteria

Patients should not enter the study if any of the following exclusion criteria are fulfilled

1. Involvement in the planning and/or conduct of the study (applies to both AstraZeneca staff and/or staff at the study site)
2. Any previous treatment with a PARP inhibitor, including olaparib.
3. Patient with any other malignancy which has been active or treated within the previous 5 years, with the exception of adequately treated cone-biopsied in situ carcinoma of the cervix uteri, endometrial carcinoma stage 1A or 1, or non-melanoma skin lesions.

- 
- Patients with a history of ovarian or breast cancer within the past 5 years are eligible in the case of adequately treated stage I or II disease without evidence of recurrence.
4. Patients receiving any systemic chemotherapy, radiotherapy (except for palliative reasons), within 2 weeks from the last dose prior to study treatment (or a longer period depending on the defined characteristics of the agents used). The patient can receive a stable dose of bisphosphonates for bone metastases, before and during the study as long as these were started at least 4 weeks prior to treatment. Prostate cancer patients may also continue to receive LHRH.
 5. Patients receiving the following classes of inhibitors of CYP3A4 (see Section 5.6.1 for guidelines and wash out periods).
 - Azole antifungals
 - Macrolide antibiotics
 - Protease inhibitors
 6. Persistent toxicities (>CTCAE grade 2), excluding alopecia, caused by previous cancer therapy.
 7. Patients with symptomatic uncontrolled brain metastases. A scan to confirm the absence of brain metastases is not required. The patient can receive a stable dose of corticosteroids before and during the study as long as these were started at least 4 weeks prior to treatment.
 8. Patients with spinal cord compression, unless they have received definitive treatment for this and have evidence of clinically stable disease for at least 28 days prior to study entry
 9. Major surgery within 2 weeks of starting study treatment and patients must have recovered from any effects of any major surgery.
 10. Patients considered a poor medical risk due to a serious, uncontrolled medical disorder, non-malignant systemic disease or active, uncontrolled infection. Examples include, but are not limited to, uncontrolled ventricular arrhythmia, recent (within 3 months) myocardial infarction, uncontrolled major seizure disorder, unstable spinal cord compression, superior vena cava syndrome, or any psychiatric disorder that prohibits obtaining informed consent.
 11. Patients unable to swallow orally administered medication and patients with gastrointestinal disorders likely to interfere with absorption of the study medication.
 12. Breast-feeding women.

13. Immunocompromised patients, eg, patients who are known to be serologically positive for human immunodeficiency virus.
14. Patients with known active hepatic disease (ie, Hepatitis B or C).
15. Patients with a known hypersensitivity to olaparib or any of the excipients of the product.
16. Patients with uncontrolled seizures.

For procedures for withdrawal of incorrectly enrolled patients see Section [5.3](#)

5. STUDY CONDUCT

5.1 Restrictions during the study

Contraception

Patients of child bearing potential and their partners, who are sexually active, must agree to the use of two highly effective forms of contraception throughout their participation in the study and for 3 months after last dose of study drug(s).

- Condom with spermicide
- and one of the following
- oral contraceptive or hormonal therapy (e.g. hormone implants)
- Placement of an intra-uterine device (see [Appendix D](#) as consideration should be given to the type of device/system used)

[Appendix D](#) provides details of acceptable birth control methods to be used within the study.

Other Concomitant treatment

1. No other chemotherapy, hormonal therapy (hormone replacement therapy is acceptable) or other novel agent is to be permitted during the course of the study for any patient (the patient can receive a stable dose of corticosteroids during the study as long as these were started at least 4 weeks prior to treatment, as per exclusion criteria above). Palliative radiotherapy is allowed for pre-existing small areas of painful metastases that cannot be managed with local or systemic analgesics as long as no evidence of disease progression is present (see section [5.6.3](#)).
2. Patients with hormone-refractory prostate cancer may continue to take LHRH agonist treatment during the study if, in the investigator's opinion, this is appropriate.

3. Live virus and bacterial vaccines should not be administered whilst the patient is receiving study medication and during the 30 day follow up period. An increased risk of infection by the administration of live virus and bacterial vaccines has been observed with conventional chemotherapy drugs and the effects with olaparib are unknown.
4. Patients should avoid concomitant use of drugs, herbal supplements and/or ingestion of foods known to modulate CYP3A4 enzyme activity and drugs that are known to be CYP3A4 substrates (see Section 5.6.1) from the time they enter the screening period until 30 days after the last dose of study medication. In vitro data have shown that the principal enzyme responsible for the formation of the 3 main metabolites of olaparib is CYP3A4 and consequently, although the contribution of metabolic clearance to total drug clearance in man is currently unknown this restriction is required to ensure patient safety.

5.2 Patient enrolment and initiation of investigational product

The principal investigator will:

1. Obtain signed informed consent from the potential patient before any study specific procedures are performed.
2. Assign potential patient a unique enrolment number, beginning with “E#”.
3. Determine patient eligibility. See Sections 4.1 and 4.2

As patients are screened for the study, they must be allocated an enrolment code (E-code). The E-code is a 7-digit number made up of the centre number and the patient number within that particular centre (eg, the first patient screened at centre number 0001 would be assigned the E-code E0001001, the second patient screened would be E0001002 and so on). This number is the patient’s unique identifier and is used to identify the patient on the Case Report Forms (CRFs).

If a patient withdraws from participation in the study, then his/her enrolment code cannot be reused.

5.2.1 Procedures for randomisation (Not Applicable)

5.3 Procedures for handling patients incorrectly enrolled

Patients who fail to meet the inclusion/exclusion criteria should not, under any circumstances, be enrolled or receive study medication. There can be no exceptions to this rule.

Where patients that do not meet the selection criteria are enrolled in error or incorrectly started on treatment, or where patients subsequently fail to meet the study criteria post-initiation, a discussion should occur between the AstraZeneca Study Delivery Team Physician and the investigator regarding whether to continue or discontinue the patient from treatment. Once a

decision is made, investigators need to ensure they comply with all applicable requirements for human patient protection and ethical review.

The AstraZeneca Study Delivery Team Physician is to ensure all such decisions are appropriately documented. In situations where an agreement cannot be reached, the patient should have their study therapy stopped and be withdrawn from the study.

5.4 Blinding and procedures for unblinding the study

5.4.1 Methods for ensuring blinding (Not Applicable)

5.4.2 Methods for unblinding the study (Not Applicable)

5.5 Treatments

5.5.1 Identity of investigational product

The Investigational Products Supply (IPS) section of AstraZeneca will supply olaparib as white, size 0 capsules.

Investigational product^a	Dosage form and strength	Manufacturer
olaparib	50 mg capsule	Patheon on behalf of AstraZeneca

^a Descriptive information for olaparib can be found in the IB.

5.5.2 Doses and treatment regimens

For all centres, olaparib will be packed in high-density polyethylene (HDPE) bottles with child-resistant closures. At each dosing visit the patient will be dispensed sufficient capsules for at least each cycle period plus overage. Olaparib will be dispensed to patients on Day 1 and every 28 days thereafter until the patient completes the study, withdraws from the study or closure of the study.

Patients will take olaparib orally twice daily at 400 mg bd continually. Eight 50 mg capsules should be taken at the same times each day, approximately 12 hours apart, morning and evening, with a glass of water.

Patients will be instructed to take their doses of olaparib at least 1 hour after food, and the patient should then refrain from eating for a further 2 hours due to potential effect of food on absorption. The olaparib capsules should be swallowed whole and not chewed, crushed, dissolved or divided.

If vomiting occurs shortly after the olaparib capsules are swallowed, the dose should only be replaced if all of the intact capsules can be seen and counted. Should any patient enrolled on the study miss a scheduled dose for whatever reason (eg, as a result of forgetting to take the capsules or vomiting), the patient will be allowed to take the scheduled dose up to a maximum of 2 hours after that scheduled dose time. If greater than 2 hours after the scheduled dose time, the missed dose is not to be taken and the patient should take their allotted dose at the next scheduled time.

Patients will continue with olaparib until objective disease progression (determined by RECIST 1.1) as long as in the investigator's opinion they are benefiting from treatment and they do not meet any other discontinuation criteria.

5.5.3 Additional study drug (Not Applicable)

5.5.4 Labelling

Labels will be prepared in accordance with Good Manufacturing Practice (GMP) and local regulatory guidelines. The labels will fulfil GMP Annex 13 requirements for labelling. Label text will be translated into local language.

Investigational Product Supplies (IPS), AstraZeneca, will label each bottle of olaparib. Each bottle will have a label permanently affixed to the outside stating that the material is for clinical trial/investigational use only and should be kept out of reach of children.

The labels will include blank lines for quantity of capsules to be taken, patient enrolment code (E-code) and date of dispensing.

5.5.5 Storage

All study drugs must be kept in a secure place under appropriate storage conditions and may only be dispensed by a pharmacist or a qualified designee. The investigational product label on the bottle and the investigator Brochure specifies the appropriate storage and shipment.

Olaparib must not be stored under refrigerated conditions.

5.5.6 Management of toxicity of olaparib (monotherapy treatment)

Any toxicity observed during the course of the study should be managed by interruption of the dose if deemed appropriate by the investigator. Repeat dose interruptions are to be allowed as required, for a maximum of 4 weeks (28 days) on each occasion. Olaparib must be interrupted until the patient recovers completely or the toxicity reverts to National Cancer Institute (NCI) Common Terminology Criteria for Adverse Events (CTCAE version 3) grade 1 or less.

Where toxicity reoccurs following re-challenge with olaparib and where further dose interruptions are considered inadequate for management of toxicity, then the patient is to be considered for dose reduction or must permanently discontinue treatment with olaparib.

Treatment must be interrupted if any NCI-CTCAE grade 3 or 4 adverse event occurs which the investigator considers to be related to administration of olaparib. If this has not resolved to at least NCI-CTCAE grade 1 during the maximum 4 weeks (28 days) dose interruption period, and/or the patient has already undergone a maximum of 2 dose reductions already, (to a minimum dose of 100 mg bd), the patient must permanently discontinue treatment with olaparib. If toxicity is appropriately resolved, then the patient should restart treatment with olaparib, but with a 50% dose reduction according to [Table 3](#). If the event recurs with the same severity, treatment should be interrupted again and, on resolution, a further dose

reduction made. If, on restarting treatment, the event continues to occur, the patient must permanently discontinue olaparib.

An exception to the management of olaparib-related toxicity is the occurrence of leukopenia and/or anaemia. In this case, the AE should be managed as deemed appropriate by the investigator (growth factor, transfusions), without interruption in study drug or change in dose. However, growth factors must be discontinued once the AE has recovered to grade 1 or better. They may be resumed, if necessary, if leukopenia/anaemia develops again and discontinued once it recovers.

The dose of olaparib must not be adjusted under any other circumstances unless the AstraZeneca physician gives prior agreement. Once the dose of olaparib has been reduced under no account should it be re-escalated.

All dose reductions and interruptions (including any missed doses), and the reasons for the reductions/interruptions are to be recorded in the eCRF.

Table 3 Dose reductions for olaparib

Reduction	Dose Level^a
Initial Dose Level	400 mg bd
1 st dose reduction due to NCI-CTCAE grade 3 or 4 treatment-related SAE/AEs	200 mg bd
2 nd dose reduction due to NCI-CTCAE grade 3 or 4 treatment-related SAE/AEs	100 mg bd
NCI-CTCAE grade 3 or 4 treatment-related SAEs/AEs	No reduction allowed – withdraw patient

^a olaparib must not be decreased below 100 mg bd

Olaparib should be stopped before surgery and restarted following recovery. No stoppage of olaparib is required for any biopsy procedures.

Olaparib should be discontinued for a minimum of 7 days before a patient undergoes therapeutic radiation treatment. This is not required where palliative doses are used.

If new or worsening pulmonary symptoms (eg, dyspnoea) or radiological abnormality occurs, an interruption in olaparib dosing is recommended and a diagnostic workup (including a high resolution CT scan) should be performed, to exclude pneumonitis. Following investigation, if no evidence of abnormality is observed on CT imaging and symptoms resolve, then olaparib treatment can be restarted, if deemed appropriate by the investigator. If significant pulmonary abnormalities are identified, these need to be discussed with the AstraZeneca Study Delivery Physician.

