5.8 Discontinuation of investigational product

Patients may be discontinued from investigational product(IP), olaparib, in the following situations:

- Patient decision. The patient is at any time free to discontinue treatment, without prejudice to further treatment
- Adverse Event
- Severe non-compliance with the study protocol
- Any CTC grade 3 or 4 events that have not reverted to CTC grade 1 or less within 4 weeks (28-days). At the investigator's discretion, following dose interruption, patients may be considered for dose reductions providing they have not already undergone the maximum number of dose reductions allowed for guidelines see section 5.5.6. However, if upon re-challenging with olaparib at the lowest reduced dose, 100 mg bd (for guidelines refer to Section 5.5.6), any CTC grade 3 or 4 adverse events recur, the patient must be discontinued.
- Objective progression according to RECIST 1.1 criteria:

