5.9 Withdrawal from study

Patients are at any time free to withdraw from study (investigational product and assessments), without prejudice to further treatment (withdrawal of consent). Such patients will always be asked about the reason(s) and the presence of any adverse events. If possible, they will be seen and assessed by an investigator. Adverse events will be followed up (See Sections 6.4.3 and 6.4.4), and study drug should be returned by the patient.

Reasons for withdrawal from the study:

- Voluntary withdrawal by the patient who is at any time free to discontinue their participation in the study, without prejudice to further treatment
- Risk to patients as judged by the investigator and/or AstraZeneca
- Severe non-compliance with the protocol as judged by the investigator and/or AstraZeneca
- Incorrectly enrolled patients ie, the patient does not meet the required inclusion/exclusion criteria for the study
- The patient becomes pregnant
- Patient lost to follow-up

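### The leukopenia/anaemia exception in Protocol 5.5.6 has no grade or duration limit and conflicts with 5.8 for severe events

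*Protocol*

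**What the plan says.** Section 5.5.6 first lets the investigator interrupt olaparib for any toxicity, for up to 28 days on each occasion. It then sets the general rule for severe related events: "Treatment must be interrupted if any NCI-CTCAE grade 3 or 4 adverse event occurs" that the investigator attributes to olaparib. After recovery the patient restarts at half the dose, following Table 3. Without recovery in 28 days, or once two reductions have been used, treatment stops permanently.

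The next paragraph exempts any occurrence of leukopenia and/or anaemia: "the AE should be managed as deemed appropriate by the investigator (growth factor, transfusions), without interruption in study drug or change in dose". The only grade it mentions concerns supportive care: "growth factors must be discontinued once the AE has recovered to grade 1 or better". A further sentence closes the list of dose changes: "The dose of olaparib must not be adjusted under any other circumstances unless the AstraZeneca physician gives prior agreement".

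Section 5.8 lists situations in which patients may be discontinued. One is "Any CTC grade 3 or 4 events that have not reverted to CTC grade 1 or less within 4 weeks". The same item allows dose reduction after an interruption, at the investigator's discretion, and refers to 5.5.6 for guidance. It ends with a mandatory rule for rechallenge at 100 mg bd: if "any CTC grade 3 or 4 adverse events recur, the patient must be discontinued". Leukopenia and anaemia are not excepted anywhere in this item. Section 5.9 separately allows withdrawal for "Risk to patients as judged by the investigator and/or AstraZeneca".

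**The concern.** An exception that keeps patients on dose through a manageable cytopenia is a legitimate choice. This one has no upper bound. It is triggered by occurrence alone, so grade 1 and grade 4 events get the same instruction, and an event that persists for months is treated like one that lasts a week. Section 1.1.9 identifies the bone marrow as the target organ of toxicity, so these are the events for which a bound matters most.

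A site that turns to 5.8 finds different instructions for the same event. Two sites could therefore treat the same grade 4 anaemia differently, each with protocol text in support. The issue is patient safety and consistent conduct. It touches no sample size, error rate or efficacy estimate.

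**Working it through.** The protocol states no figure to reproduce, so the check sets the provisions side by side and adds the dose arithmetic.

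**Related grade 3 or 4 events under each provision**

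| Provision | Any other event | Leukopenia or anaemia |
|---|---|---|
| 5.5.6, interruption | Mandatory, at most 28 days | Not to be interrupted |
| 5.5.6, dose on restart | Halved, per Table 3 | Unchanged |
| 5.5.6, limit for olaparib | Stop if unresolved at 28 days or after two reductions | None stated |
| 5.8, unresolved at 28 days | May be discontinued | Same wording, no carve-out |
| 5.8, reduction after interruption | At investigator's discretion | Same wording, no carve-out |
| 5.8, recurrence at 100 mg bd | Must be discontinued | Same wording, no carve-out |

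The last two columns differ in the first three rows, which come from 5.5.6. They agree in the last three, which come from 5.8. That is the conflict.

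**Is there a hidden limit in the exception?** Its one threshold, grade 1 or better, says when growth factors stop. It says nothing about olaparib. No other sentence in the paragraph carries a grade, a time or a recurrence count.

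**Dose arithmetic (doses from Table 3)**

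- Starting dose: 400 mg × 2 = 800 mg/day.
- General rule after one related grade 3 or 4 event: 200 mg × 2 = 400 mg/day, after a hold of up to 28 days.
- Exception: 800 mg/day throughout. Ratio 800 / 400 = 2.
- Dose floor: 100 mg × 2 = 200 mg/day; 200 / 800 = 25% of the starting dose.

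**Reach of the conflict at 100 mg bd.** If 5.5.6 is followed, leukopenia and anaemia do not themselves trigger a reduction. A patient ordinarily reaches 100 mg bd through two reductions for some other toxicity, so this part of the conflict concerns few patients. The unlimited exception at 400 mg bd applies to everyone treated.

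**How many patients?** The protocol gives no rate of grade 3 or 4 leukopenia or anaemia. Section 1.1.10 describes anaemia as generally grade 1 or 2 and neutropenia as predominantly so, which suggests a small number.

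**The case against.** The best defence is that the exception is deliberate and softer than it looks. It says that these events should, not must, be managed this way, and it leaves the means to the investigator. The prior-agreement sentence concerns adjusting the dose and does not name interruption. Section 5.8 covers any grade 3 or 4 event and mentions discretionary reduction after a hold. Anaemia needing transfusion is among the Appendix B examples of events usually considered serious, so it should reach the sponsor by the end of the next business day under 6.4.4. The clinical data behind the exception are in the Investigators' Brochure, which is not available here.

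Much of this stands, and it rules out a stronger reading. A reader might infer that nothing lies between unchanged dose and permanent stop. The documents do not support that: the 5.8 wording leaves a discretionary reduction arguable, and a temporary hold is not plainly forbidden. It is only arguable because 5.8 speaks of reduction following an interruption and refers back to 5.5.6, which says not to interrupt for these events.

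A reader might also see a contradiction with the last row of Table 3 ("No reduction allowed – withdraw patient"). That is minor, because the table is invoked only by the general rule from which the exception departs. Nor is section 1.3 clearly contradicted. It promises directions for unmanageable toxicity without saying that they must stand in 5.5.6, and 5.8 and 5.9 provide ways to stop.

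The defence does not supply a limit in 5.5.6. Prompt SAE reporting informs the sponsor but does not tell the site what to do with the dose. If 5.8 is meant to govern severe cytopenia, 5.5.6 gives the opposite instruction; if it is not, no bound exists.

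**Conclusion.** The point holds as an unlimited exception in 5.5.6 and a conflict with 5.8 for severe leukopenia or anaemia. A site that follows 5.5.6 keeps dosing through a related grade 4 event in the known target organ, at twice the daily dose that the general rule would allow on restart. That factor of two describes the rule and does not measure harm.

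Permanent discontinuation under 5.8 or 5.9, a change agreed beforehand with the sponsor's physician, and arguably a discretionary reduction under 5.8 all remain open. The conclusion rests on reading the exception as covering every grade, which its wording does. The number of patients affected cannot be derived from the protocol and is probably small. This is a cheap improvement with a bearing on patient safety.

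**What to change.** In 5.5.6, end the exception when the event reaches grade 4, or when it has not returned to grade 1 or less within 28 days despite supportive care. After that point the general interruption and reduction rule applies. The 28 days match the limit already used in 5.5.6 and 5.8. The grade 4 limit is a proposal with no figure in the protocol behind it, so the sponsor's physicians should confirm the threshold.

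In 5.8, add a sentence that its grade 3 and 4 provisions, including the mandatory stop at 100 mg bd, apply to leukopenia and anaemia beyond that limit. Table 3 needs no essential change, since the general rule would then lead to it.

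The cost is a wording amendment to two sections and a notification to sites. No new assessments are needed, because 6.4.5 already requires haematology at each visit. The downside is a few more interruptions or reductions for severe cytopenia.
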